11.7. Procedures for Reporting any Deviation(s) from the Original Statistical Plan

The trial protocol will be made available to reviewers of any publication arising from this study. Any amendments to the original protocol or additional analysis not previously specified in the protocol will also be made available to reviewers.

12. DATA MANAGEMENT

12.1. Source Data

Source documents will be the hospital records for the basic demographics and HbA1c level. During the trial they will be the patient diaries, both during the run-in week and for the trial week. This is where data is first recorded, and from which participants' CRF data are obtained.

CRF entries will be considered source data if the CRF is the site of the original recording (e.g. there is no other written or electronic record of data). All documents will be stored safely in confidential conditions. On all trial-specific documents, other than the signed consent, the participant will be referred to by the trial participant number/code, not by name.

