Participants will be asked not to give a correction dose before the meal if the BG level is between 7-12mmol/l as this would interfere with the analysis. They will be asked, if possible, not to carry out the test meals if their pre-meal BG is greater than 12 mmol/l. But if they have to do the test meal with a high pre-meal BG (above 12 mmol/l) they will be instructed to give their usual correction bolus in addition to the prescribed insulin dose for the test meal. This data will be analysed separately. If BG is below 4mmol/l (hypoglycaemic) or above 16mmol/l participants will be asked to abandon the study evening and repeat on another evening. Full written instructions will be provided to the family for all aspects of the insulin dosing for the study meals.

During the study on the standardised meal days children will be instructed not to eat any food after the meal during the evening, and not to correct any later BG levels unless they are dangerously high (BG over 16 mmol/l with ketones over 0.5 mmol/l). If BG levels go low at any time (BG less than 4 mmol/l) children will be instructed to treat the hypoglycaemia according to their usual management, and omit

any further study doses of insulin if the hypoglycaemia occurs after a first study dose and a second is due. This data will be analysed separately. Children and families will be asked to complete diaries during the trial week.

At the end of the study period (the day after the third meal), children will come back to the research facility or clinic for the end of study visit (visit 3). A research nurse or dietitian will remove the CGM sensor and download the data onto a secure laptop. Children and their families will then be asked to complete a short questionnaire about the acceptability of using the extra insulin doses, and their perceptions as to whether there were any beneficial or adverse effects.

The study dietitian will calculate standard outcomes from each patient's sensor download and pass on anonymously to the study statistician to analyse the data.

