8.5. Subsequent Visits

Visit 2 – Study visit

- A review of the BG levels in the preceding week will be carried out by the study dietitian, in order to determine whether any further adjustments in insulin dose need to be made.
- The CGM will be inserted.
- Randomisation of the insulin dose order will be carried out and final dose calculations will be done by the dietitian according to the equations in section 5.3.
- Full written instructions will be provided to the participants, including insulin doses and timings for the three study meals, contact details and what to do if BG levels should be high (greater than 16mmol/L) or low (less than 4mmol/L).
- There will also be instructions about what they should do in the event of a sensor malfunction.
- The child and family will be informed that they can call the research team during office hours at any stage to discuss events during the week of the study, and they will be provided with contact details. If any advice is required outside office hours, they will be advised to contact their clinical diabetes team in the usual way.

Visit 3: End of study visit - The participant will return to their original outpatient or day-care setting and the CGM sensor will be removed by the study nurse and data downloaded onto the web-based system Diasend which is regularly used in clinics. Participants and their family will have the opportunity of viewing the download from the sensor. The participant and parent will be asked to complete the short questionnaires about the acceptability of the additional insulin doses.

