11.4. Criteria for the Termination of the Trial

We would only anticipate 10 episodes of severe hypoglycaemia in 340 patients per year. Therefore the likelihood of a severe hypo occurring during this study under normal circumstances would be very small. So if we assume there is no increase in risk then we would only expect to see 2 severe hypos in one of the two arms in 3 out of every 10,000 trials, for a single hypo in either arm this increases to about 1 in every 100 trials. Therefore we would terminate the trial if we had 2 severe hypos occurring on any arm of the trial.

11.5. Procedure for Accounting for Missing, Unused, and Spurious Data.

We will use boxplots to identify outlying, unusual or spurious data using pre-defined decision rules (e.g. upper or lower quartiles $\pm 1.5 \times \text{IQR}$). In the case of implausible or unlikely outcome data we will look back at CRF's to rule out data handling errors. If outliers cannot be resolved then we will exclude this particular result from the main analysis. We intend to use a complete case analysis but we will conduct a sensitivity analysis to assess the impact of any missing data using appropriate multiple imputation methods.

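### Sections 12.1 and 11.5 omit the CGM download from the source list and from the check on implausible outcomes, so a correctable or genuine extreme glucose value may be excluded

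*Combined protocol and SAP*

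**What the plan says.** **Source documents (12.1).** Demographics and HbA1c come from hospital records. For the rest of the trial data: "During the trial they will be the patient diaries, both during the run-in week and for the trial week". The section continues: "This is where data is first recorded, and from which participants' CRF data are obtained". It allows one exception: "CRF entries will be considered source data if the CRF is the site of the original recording", with the absence of any other written or electronic record as its example. The CGM download is not mentioned.

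**Check on odd values (11.5).** Boxplots flag unusual results, with quartiles ± 1.5 × IQR as the example rule. Then: "In the case of implausible or unlikely outcome data we will look back at CRF's to rule out data handling errors". A result that cannot be resolved is left out of the main analysis. The main analysis is complete-case, with multiple imputation as a sensitivity analysis.

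**Where the outcomes come from (Synopsis, 5, 6.3).** The primary outcome is the mean glucose excursion over the 8 hours after the test meal, taken from CGM profiles. The secondary glucose outcomes also come from CGM profiles. Under 6.3 the dietitian calculates the outcomes from each "sensor download and pass on anonymously to the study statistician to analyse the data".

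**Where the download goes.** Section 6.3 has staff "download the data onto a secure laptop". Section 8.5 has "data downloaded onto the web-based system Diasend which is regularly used in clinics".

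**The concern.** The record used for checking is not the record from which the outcome is made. The data-handling step most open to error here is the dietitian's derivation: finding the evening in a week-long trace, setting the start of the window, taking the baseline, truncating the profile where 11.6 requires it, and averaging. Families choose their own evenings and repeat abandoned ones (6.3), so this cannot be read off a fixed calendar. Section 11.5 asks nobody to reopen the trace or repeat the calculation.

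Two kinds of flagged value are then at risk. One is wrong but could be put right from the trace. The other is extreme but true. If the CRF cannot settle the matter, the written rule removes either from the main analysis. Losing the first wastes data. Losing the second also makes the observed spread smaller than it really is and may shift a timing mean.

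**Working it through.** The plan gives no figure on this point to reproduce. The check has two parts.

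**1. Following the data**

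The path is: sensor → download (6.3, 8.5) → dietitian's derived outcomes (6.3) → paper CRF and/or Excel (12.3) → statistician → check under 11.5.

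- *Does the CRF exception in 12.1 cover the trace?* No. It applies where the CRF is the original recording, and the trace already exists electronically.
- *How much data lies behind one primary outcome value?* Section 6.3 gives a reading every 5 minutes: 60/5 = 12 per hour, and 12 × 8 = 96 readings per meal. The diary finger-pricks are pre-meal, bedtime and waking (6.3), which is too few to confirm a mean of 96 readings.
- *What can a diary-based CRF show?* The randomised schedule is part of the diary (8.3). Actual doses are recorded, and timing is judged to within 15 minutes (9.3). It can therefore help reveal a wrong evening, dose time or baseline.
- *What if the derived outcome is itself on the CRF, as 12.3 allows?* Looking back then finds a transcription slip between CRF and spreadsheet. A slip made in the derivation would appear identically in both places.

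**2. Would the check be used?**

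Inputs: 36 children (needed) or 40 (recruited) from 11.2, three meals each, so 3 × 36 = 108 or 3 × 40 = 120 meal values; and the 1.5 × IQR example from 11.5.

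Assumptions: error-free data, fences set separately within each timing, and the three timings treated as independent. The documents give no outcome distribution, so three were tried, with 50,000 simulated samples each.

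A value is flagged if it lies below Q1 − 1.5 × IQR or above Q3 + 1.5 × IQR. Expected flags = 3 × mean flags per timing. P(at least one) = 1 − P(none in one timing)³.

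| Distribution | Children | Flags per timing | Flags in trial | P(at least one) |
|---|---|---|---|---|
| Normal | 36 | 0.579 | 1.74 | 0.736 |
| Normal | 40 | 0.604 | 1.81 | 0.751 |
| t, 5 df | 36 | 1.491 | 4.47 | 0.982 |
| t, 5 df | 40 | 1.622 | 4.87 | 0.987 |
| Lognormal, sigma 0.5 | 36 | 1.525 | 4.58 | 0.989 |
| Lognormal, sigma 0.5 | 40 | 1.677 | 5.03 | 0.993 |

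For comparison, with known normal quartiles the fences lie at 4 × 0.6745 = 2.698 SD. The flag rate is then 0.00698, or 0.75 of 108 and 0.84 of 120 values. Estimating the quartiles from 36–40 children raises this to 1.7–1.8.

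**Cost of one exclusion.** With pairwise comparisons, one lost meal removes one child from both comparisons that use that timing: 1/40 = 2.5% of pairs, or 1/36 = 2.8%.

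**The case against.** The strongest reply is that this is a gap in wording over data that are kept. The download exists, and nothing in 11.5 forbids opening it before declaring a value unresolved. Section 11.1 has the chief investigator, dietitian and statistician work through the glucose records, and Section 13 adds sponsor monitoring. This stands to the extent that no data are lost and a careful team might do the right thing anyway. But 11.1 does not describe a verification step, and the one rule written for implausible values points to the CRF and ends in exclusion.

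A reader might infer more than the documents support:

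- *That the check can find no error in the primary outcome.* The diary holds the schedule and the doses given, finger-pricks cross-check the baseline, and derived values may be on a CRF. Some errors could be found.
- *That all glucose outcomes are sensor-only.* The tertiary hypo- and hyperglycaemia outcome in Section 5 also accepts self-monitored readings.
- *That this is the sole safeguard on the data.* Sections 11.1 and 13 provide others, though less specific.
- *That mislabelled evenings dilute the timing effect by a calculable amount.* No error rate is given. The 2 mmol/L in 11.2 refers to the 5-hour excursion, not the 8-hour primary outcome. With three timings, swapping two evenings reverses only one of the three contrasts. Such swaps need not be outliers, so checking flagged values would not find them.
- *That 6.3 and 8.5 contradict each other on storage.* A download may go both to a laptop and to the web system. What is missing is a statement of which copy is the retained record.

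**Conclusion.** The point holds as a defect in the written check-and-exclude rule. The CGM download, from which the primary and secondary glucose outcomes are calculated, is neither a listed source document nor the record consulted when an outcome looks implausible. A diary-based CRF cannot verify the trace or the calculation of the 8-hour mean excursion, so correctable or genuine extreme values may be removed from the main analysis.

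The rule would probably be used. With no errors at all, roughly 2 to 5 of 108–120 meal values would be flagged, and the chance of at least one flag runs from about 74% (normal) to about 99% (skewed). These figures rest on the assumed distributions, independent timings, fences set within timing, and adoption of the example 1.5 × IQR rule. They count flags, not exclusions. How many flagged values would actually be lost, and with what effect on the timing comparison, cannot be worked out from the documents.

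**What to change.** **Section 12.1.** Name each participant's time-stamped CGM download as the source document for the sensor-based outcomes, and state where the retained copy is kept, so that 6.3 and 8.5 can be read together.

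**Section 11.5.** Replace the CRF look-back with this sequence, to be completed before any outlier is excluded:

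1. Re-derive the flagged value from the download, using the diary meal and dose times and the randomised order.
2. If an error is found, correct the value and record the correction.
3. If the trace and derivation are sound, keep the value in the main analysis.
4. Exclude it only if the sensor record itself is faulty.

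This governs outliers only. The separate removal rules in 9.3 and 11.6 are untouched.

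The cost is a few sentences of protocol text and a few minutes per flagged value, with no new data. The change does not detect errors that stay inside the boxplot fences.

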12.2. Access to Data

Direct access will be granted to authorised representatives from the Sponsor, host institution and the regulatory authorities to permit trial-related monitoring, audits and inspections.

12.3. Data Recording and Record Keeping

All trial data will be entered on to paper CRFs and/or a to an Excel spreadsheet (Microsoft Office).

The participants will be identified by a unique trial specific number and/or code in any database. The name and any other identifying detail will NOT be included in any trial data electronic file.

All study data will be held until the last participant has reached the age of 21 or up to 5 years from the end of the trial, whichever is the later date.

13. QUALITY ASSURANCE PROCEDURES

Regular monitoring will be performed by authorised individuals from the sponsor according to GCP.

14. SERIOUS BREACHES

The Medicines for Human Use (Clinical Trials) Regulations contain a requirement for the notification of "serious breaches" to the MHRA within 7 days of the Sponsor becoming aware of the breach.

A serious breach is defined as "A breach of GCP or the trial protocol which is likely to affect to a significant degree –

- (a) the safety or physical or mental integrity of the subjects of the trial; or
- (b) the scientific value of the trial".

In the event that a serious breach is suspected the Sponsor must be contacted within 1 working day. In collaboration with the C.I., the serious breach will be reviewed by the Sponsor and, if appropriate, the Sponsor will report it to the REC committee, Regulatory authority and the NHS host organisation within seven calendar days.

15. ETHICAL AND REGULATORY CONSIDERATIONS

15.1. Declaration of Helsinki

The Investigator will ensure that this trial is conducted in accordance with the principles of the Declaration of Helsinki.

15.2. Guidelines for Good Clinical Practice

The Investigator will ensure that this trial is conducted in accordance with relevant regulations and with Good Clinical Practice.

15.3. Approvals

The protocol, informed consent form, participant information sheet and any proposed advertising material will be submitted to an appropriate Research Ethics Committee (REC), regulatory authorities (MHRA in the UK), and host institution(s) for written approval.

The Investigator will submit and, where necessary, obtain approval from the above parties for all substantial amendments to the original approved documents.

15.4. Reporting

The CI shall submit once a year throughout the clinical trial, or on request, an Annual Progress Report to the REC, host organisation and Sponsor. In addition, an End of Trial notification and final report will be submitted to the MHRA, the REC, host organisation and Sponsor.

15.5. Participant Confidentiality

The trial staff will ensure that the participants' anonymity is maintained. The participants will be identified only by a participant ID number on all trial documents and any electronic database, with the exception of the CRF, where participant initials may be added. All documents will be stored securely and only accessible by trial staff and authorised personnel. The trial will comply with the Data Protection Act, which requires data to be anonymised as soon as it is practical to do so.

15.6. Expenses and Benefits

Reasonable travel expenses for any visits additional to normal care will be reimbursed on production of receipts, or a mileage allowance provided as appropriate.

The test meals will be provided by the service, and a funding application has been made for these. In addition, if funding is granted, each child will be offered a £10 high street voucher in return for their help with the study.

15.7. Other Ethical Considerations

The use of Children

The participation of children and young people is indispensable for this study because there is a lack of research on the appropriate dietary management of children and adolescents with Type 1 diabetes using MDI. Adult data cannot be extrapolated to children because of their very different life-styles, body size, insulin requirements and dietary differences. Evidence based dietary interventions for children need to be examined in the paediatric population. In particular, the acceptability for giving additional insulin injections at meal-times may be very different in children compared to adults.

Consent

It is important that both the child and parent/legal guardian has an adequate opportunity to ask questions, and to fully understand the implications of the study before agreeing to take part. Children's wishes will not be over-ridden. The leaflets and discussion will make it clear that withdrawal from the study can occur at any time with no disadvantage in terms of normal medical care.

16. FINANCE AND INSURANCE

16.1. Funding

Part-funding for the study has been received from the NovoNordisk Research Foundation. Additional funding has been provided by the OUH Research Capability Funding to employ a Dietitian for one day per week for a year. A research nurse is employed within the department.

16.2. Insurance

NHS bodies are legally liable for the negligent acts and omissions of their employees. If you are harmed whilst taking part in a clinical trial as a result of negligence on the part of a member of the trial team this liability cover would apply.

Non-negligent harm is not covered by the NHS indemnity scheme. The Oxford University NHS Trust, therefore, cannot agree in advance to pay compensation in these circumstances.

In exceptional circumstances an ex-gratia payment may be offered.

17. PUBLICATION POLICY

The Investigators will be involved in reviewing drafts of the manuscripts, abstracts, press releases and any other publications arising from the study. Authors will acknowledge that the study was funded by the body which provided the funding. Authorship will be determined in accordance with the ICMJE guidelines and other contributors will be acknowledged.

Study results will be disseminated to research participants by the usual clinic newsletter and by presenting the results to the Parents' support group (Oxfordshire Young Diabetics) open meeting, and to similar groups in other participating hospitals.

19. APPENDIX A: SCHEDULE OF PROCEDURES

Procedures	Visit 1	Telephone	Telephone	Visit 2	Visit 3
	Day 0	call day 3-4	call Day 5-6	Day 7-10	Day 14-16
	Screening			Baseline	
Informed consent/assent	X				
Demographics	X				
Medical history	X				
HbA1c measurement if not done in last 3 months	X				
Eligibility assessment	X				
Provide diaries for run-in week	X				
Dietitian to order standard meals	X				
Assessment ICR		X		X	
Optimise ICR			X		
Randomisation				X	
Insert CGM				X	
Explain trial insulin doses				X	
Provide diaries and all instructions for trial week				X	
Provide contact details for trial week				X	
Remove CGM and show download to family					X
Questionnaires to participant and					X

parent/carer					
Adverse event assessments					X

20. APPENDIX B: AMENDMENT HISTORY

Amendment No.	Protocol Version No.	Date issued	Author(s) of changes	Details of Changes made
1	2	20/11/15	[name]	Minor typographical errors Additional Research Nurses added Confirmed protocol met REC recommendations to remove patient initials from all data collection
2	3	21/6/16	[name]	Adjusted the original calculation used in the protocol. This reduces the amount of additional insulin administered for fat and protein and therefore reduces the risk of hypoglycaemia in future participants. (Page 8 and Page 11) We also changed guidance for completing the study evenings following hypoglycaemic episodes immediately before the study meal – stating that in this incidence the meal should be abandoned. This also reduces the risk of hypoglycaemia afterwards. (Page 12) Minor changes were made to the flowchart to remove giving the voucher at visit 3 – this will now happen once all participants have completed the study at the end (Page 10)
3	4	1/4/17	[name]	Change of Chief Investigator
3	4	1/4/17	[name]	Clarification that the second insulin dose should be given at a time interval after the first insulin dose as there had been ambiguity from participants about the meaning of 'after the meal' Change in management of correction doses pre-evening meal. It has

				become clear that it will be very difficult to analyse change in BG level from pre-meal levels once a correction dose of insulin is given. So we have asked participants only to correct if BG above 12mmol/l and if possible to avoid doing the study on evenings when BG is above 12 mmol/l before the meal if possible. They should definitely not complete the meal if BG is above 16mmol/l
--	--	--	--	---

Protocol amendments must be submitted to the Sponsor for approval prior to submission to the REC committee or MHRA.
